11.2.2. Baseline Definition & Derivations**11.2.2.1. Baseline Definitions****Group A:**

	Study Assessments Considered as Baseline				Baseline Used in Data Display
	Screening	Day -15	Day -13 to Day -1	Day 1 (Pre-Dose)	
Safety					
Vital Signs	X	X		X	Day 1 ^[1]
Safety Lab Samples	X	X	X		Day 1
12-lead ECG	X			X	Day 1
Pharmacodynamic					
Skin Biopsy (IFN, mRNA, IFN proteins, pSYK and SYK proteins, immune cell proteins)				X	Day 1 (Lesion B will be used as baseline)
Efficacy					
RCLASI and components				X	Day 1
Pharmacokinetic					
Plasma PK				X	Day 1

NOTES :

- [1] Unless otherwise stated, the mean of replicate assessments at any given time point will be used as the value for that time point.

Group B:

	Study Assessments Considered as Baseline			Baseline Used in Data Display
	Screening	Day -5 to Day -3	Day 1 (Pre-Dose)	
Safety				
Vital Signs	X	X		Day -5 to Day -3 [1]
Safety Lab Samples	X	X	X	Day 1
12-lead ECG	X		X	Day 1
Pharmacodynamic				
Skin Biopsy (IFN, mRNA, IFN proteins, pSYK and SYK proteins, immune cell proteins)		X		Day -5 to Day -3
Efficacy				
RCLASI and components			X	Day 1
Pharmacokinetics				
Plasma PK			X	Day 1

NOTES :

- Unless otherwise stated, the mean of replicate assessments at any given time point will be used as the value for that time point.

11.2.2.2. Derivations and Handling of Missing Baseline Data

Definition	Reporting Details
Change from Baseline	= Post-Dose Visit Value – Baseline
% Change from Baseline	= $100 \times [(Post-Dose Visit Value - Baseline) / Baseline]$

NOTES :

- Unless otherwise specified, the baseline definitions specified in Section 11.2.2.1 Baseline Definitions will be used for derivations for endpoints / parameters and indicated on summaries and listings.
- Unless otherwise stated, if baseline data is missing no derivation will be performed and will be set to missing.
- The baseline definition will be footnoted on all change from baseline displays.

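### In Group B, a missing Day 1 laboratory sample or ECG leaves that subject with no change from baseline and no change-only flags for that assessment, although earlier scheduled pre-dose values exist

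*SAP*

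**What the plan says.** The Group B table in SAP 11.2.2.1 lists several pre-dose visits under the heading "Study Assessments Considered as Baseline" and then, in a last column, the single visit used in displays. The rows read "Safety Lab Samples X X X Day 1" for laboratory tests and "12-lead ECG X X Day 1" for ECG. Vital signs use Day -5 to -3 and RCLASI uses Day 1.

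SAP 11.2.2.2 makes that last column binding: "the baseline definitions specified in Section 11.2.2.1 Baseline Definitions will be used for derivations for endpoints / parameters". It then says what happens when the named value is absent: "Unless otherwise stated, if baseline data is missing no derivation will be performed and will be set to missing". Nothing in the SAP states otherwise for safety parameters, and no text says when the other listed visits would serve as baseline.

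SAP 11.5.1 defines the low flags for haemoglobin (fall of more than 25 g/L) and haematocrit (fall of more than 0.075), and the only creatinine flag (rise of more than 44.2 umol/L), as change from baseline. SAP 11.5.2 has a QTc-increase flag (more than 30 msec) beside an absolute one (more than 450 msec).

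**The concern.** Laboratory tests and ECG are named in the primary endpoint. The table presents the earlier visits as baseline candidates, but the rule never uses them. If a Day 1 haematology tube is haemolysed, the subject has no haemoglobin change at Day 14, Day 28 or follow-up, even with a valid sample from a few days earlier. Haemoglobin has no absolute low limit, so a fall in that subject cannot be flagged. The same holds for a creatinine rise after a lost chemistry sample.

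The gap reaches the listings too. Laboratory listings 23 to 26 in SAP Appendix 8 cover only subjects with abnormal values, or the abnormal values themselves. There is no listing of all laboratory data. A fall or rise that is not flagged may therefore appear in no individual listing.

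**Working it through.** **1. Pre-dose visits against the named baseline** (Group B; Protocol 7.1.3, SAP 11.1.4 and 11.2.2.1). Group A had no randomised subjects and has no change tables (SAP 2.1).

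| Assessment | Scheduled pre-dose visits | Named baseline | Earlier values not used |
|---|---|---|---|
| Laboratory tests | Screening, Day -5 to -3, Day 1 | Day 1 | 2 |
| ECG | Screening, Day 1 | Day 1 | 1 |
| Vital signs | Screening, Day -5 to -3 | Day -5 to -3 | 1 |
| RCLASI | Day 1 | Day 1 | 0 |
| Skin biopsies | Day -5 to -3 | Day -5 to -3 | 0 |

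A repeat draw is not stated to fill the gap, because SAP 11.2.3 keeps unscheduled visits out of summary tables and figures.

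**2. What one missing Day 1 assessment removes for a subject.**
- Haematology: Table 2.7 and the haemoglobin-fall and haematocrit-fall flags.
- Chemistry: Table 2.5 and the creatinine-rise flag.
- Urine: Table 2.9; no change-only flag depends on it.
- ECG: Tables 2.15 and 2.16 and the QTc-increase flag. Protocol 7.4.5 requires triplicate tracings, and SAP 11.2.2.1 says "the mean of replicate assessments at any given time point will be used as the value for that time point", so this needs all tracings to be lost.

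**3. Count of change-from-baseline tables for Group B** (SAP 11.8). There are 10: 2.5, 2.7, 2.9, 2.15, 2.16, 2.17, 2.19, 3.1, 5.4 and 5.5. Six rest on Day 1 (three laboratory, two ECG, one RCLASI). Three rest on Day -5 to -3 (vital signs, immunohistochemistry, histopathology). Table 2.19 (irritation score) has no baseline visit in SAP 11.2.2.1. One lost laboratory specimen affects 1 of 10 tables, and 3 of 10 if blood for both panels and urine are all lost.

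**4. Effect on the summaries.** Protocol 9.2.1 gives an upper limit of 21% for 0 events in 15. Under its flat Beta(1,1) prior the posterior is Beta(1, n+1), with upper 97.5% point 1 − 0.025^(1/(n+1)).
- n = 15: 1 − 0.025^(1/16) = 20.6%, which reproduces the 21%.
- n = 14: 1 − 0.025^(1/15) = 21.8%, a rise of 1.2 points.

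For a mean change at equal SD, the 95% half-width in SD units is t/√n: 0.554 at n = 15 and 0.577 at n = 14. The ratio is 1.04, so the interval is about 4% wider.

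**5. How often it might happen.** The documents give no rate of unusable samples. For an assumed rate p per subject, the chance that at least one of 15 lacks a given Day 1 value is 1 − (1 − p)^15:

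| Assumed p | Chance of at least one |
|---|---|
| 1% | 14% |
| 2% | 26% |
| 5% | 54% |
| 10% | 79% |

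**The case against.** A single named visit, footnoted on every change display as SAP 11.2.2.2 requires, is a transparent choice, and the safety analysis is descriptive. Much of the safety picture survives a lost baseline. Tables 2.6 and 2.8 set results against the normal range, the absolute laboratory and QTc flags still operate, and Table 2.14 reports maximum emergent QTc. Outside the displays, laboratory values that worsen and are judged clinically significant are adverse events (Protocol 12.3.1), and the Safety Review Team reviews laboratory data during the study (Protocol 10.8). All of this stands, and it limits the point to a display and data-handling weakness. It does not restore the change-only flags: the absolute low limit for red cell count is only a partial substitute for haemoglobin and haematocrit, and creatinine has no absolute limit in SAP 11.5.1.

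Falling back also has a cost for ECG. The only earlier tracing is from Screening, up to 28 days before, when subjects with QTcF above 450 msec (480 msec with bundle branch block) were excluded. A baseline selected to lie below a limit may overstate later increases. This stands as a caveat to be disclosed.

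A reader might infer that one lost Day 1 sample removes the subject from every change table, or takes away all four flags and one fifteenth of the safety data. The documents do not support that. Vital signs and biopsies do not use Day 1, a lost blood sample does not touch ECG or RCLASI, and the four flags come from three separate assessments. Adverse events, local tolerability and absolute values remain.

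**Conclusion.** The point holds for Group B laboratory tests and, with the selection caveat, for ECG. The SAP states a rule that discards usable scheduled pre-dose values, and the cost falls on the individual subject's change-only flags more than on the summaries. It is a minor weakness that is cheap to repair. The same missing fallback applies to vital signs, through Day -5 to -3 and not Day 1. No fallback could help RCLASI or the biopsy endpoints, which have one pre-dose visit each.

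The conclusion about the rule rests on the SAP text alone. The sizes in step 4 assume the planned 15 subjects and one lost baseline; the SAP calls the number of patients small without giving it. The likelihoods in step 5 rest wholly on an assumed loss rate and show only that the event is plausible.

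**What to change.** In SAP 11.2.2.1 and 11.2.2.2, define baseline for safety parameters as the last non-missing scheduled pre-dose value, taking the named visit first:
- laboratory tests: Day 1, else Day -5 to -3, else Screening;
- ECG: Day 1, else Screening;
- vital signs: Day -5 to -3, else Screening (Group B has no scheduled Day 1 vital signs).

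Keep the set-to-missing rule, but apply it only when no scheduled pre-dose value exists. Footnote each subject whose baseline is not the planned visit. For ECG, also note that a Screening value was subject to the QTcF eligibility limit and may overstate increases.

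The cost is a sentence or two of SAP text and a small programming change, with no new data. Results for subjects who have the planned baseline do not change. The drawback is an occasional older baseline, visible in the footnote. Settle the rule before database freeze so that it cannot appear to be chosen in response to the data.

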11.2.3. Reporting Process & Standards

Reporting Process	
Software	

 The currently supported versions of SAS software will be used to perform all data analyses and generation of displays. 	
Reporting Area	
HARP Server	:us1salx00259
HARP Area	:\\us1salx00259\\arprod\\gsk2646264\\mid204860\\final_01
QC Spreadsheet	:\\us1salx00259\\arprod\\gsk2646264\\mid204860\\final_01\\document
Analysis Datasets	

 Analysis datasets will be created according to Legacy GSK A&R dataset standards 	
Generation of RTF Files	

 RTF files will be generated for listings and tables PDF files will be generated for figures 	

Reporting Standards	
General	

 The current GSK Integrated Data Standards Library (IDSL) will be applied for reporting, unless otherwise stated: 
 4.03 to 4.23: General Principles 5.01 to 5.08: Principles Related to Data Listings 6.01 to 6.11: Principles Related to Summary Tables 7.01 to 7.13: Principles Related to Graphics 	
Formats	

 All data will be reported according to the actual treatment the subject received unless otherwise stated. GSK IDSL Statistical Principles (5.03 & 6.06.3) for decimal places (DP's) will be adopted for reporting of data based on the raw data collected. Numeric data will be reported at the precision collected on the eCRF. The reported precision from non eCRF sources will follow the IDSL statistical principles but 	

Reporting Standards	
may be adjusted to a clinically interpretable number of DP's.	
Planned and Actual Time	

 • Reporting for tables, figures and formal statistical analyses : 
 • Planned time relative to dosing will be used in figures, summaries, statistical analyses and calculation of any derived parameters, unless otherwise stated. • The impact of any major deviation from the planned assessment times and/or scheduled visit days on the analyses and interpretation of the results will be assessed as appropriate. • Reporting for Data Listings: 
 • Planned and actual time relative to study drug dosing will be shown in listings (Refer to IDSL Statistical Principle 5.05.1). • Unscheduled or unplanned readings will be presented within the subject's listings. • Visits outside the protocol defined time-windows (i.e. recorded as protocol deviations) will be included in listings but omitted from figures, summaries and statistical analyses. 	
Unscheduled Visits	

 • Unscheduled visits will not be included in summary tables. • Unscheduled visits will not be included in figures. • All unscheduled visits will be included in listings. 	
Descriptive Summary Statistics	
Continuous Data	Refer to IDSL Statistical Principle 6.06.1
Categorical Data	N, n, frequency, %
Reporting of Pharmacokinetic Concentration Data	
Descriptive Summary Statistics	Refer to IDSL Statistical Principle 6.06.1 Assign zero to NQ values (Refer to GUI_51487 for further details)
Reporting of Pharmacokinetic Parameters	
Descriptive Summary Statistics (Log Transformed)	N, n, geometric mean, 95% CI of geometric mean, standard deviation (SD) of logged data and between geometric coefficient of variation (CV _{b/w} (%)) will be reported. [1] CV _b (%) = $\sqrt{(\exp(SD^2) - 1) * 100}$ (SD = SD of log transformed data) [2] CV _w (%) = $\sqrt{(\exp(MSE) - 1) * 100}$ (MSE = mean square error from mixed effect model of loge-transformed data).
Graphical Displays	

 • Refer to IDSL Statistical Principals 7.01 to 7.13. 	

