
 
To determine the effect of GSK2646264 on the reduction in clinical activity score from baseline in treated PV and existing CLE lesions
 
To evaluate the plasma concentrations of GSK2646264 in patients with CLE
 
To determine the effect of GSK2646264 on expression of IFN mRNA signature in skin biopsies in treated PV and existing CLE lesions
 
	
 
Change from baseline of components of a modified RCLASI- composite clinical activity score at day 14 and day 28 in PV and existing lesions in erythema, oedema, dyspigmentation (and scaling in existing CLE lesions only)
 
PK parameters will be summarised
 
Change from baseline in IFN mRNA signature in skin biopsies at day 28 in PV and existing CLE lesions
 

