#### 5.5. Subject and Study Completion

A completed subject will be defined as a subject who receives at least 25 days of study drug and completes the end of treatment biopsy and assessment. Patients will be followed as per the Time & Events table, Section [7.1](#) until complete resolution of induced PV lesions.

The end of the study is defined as the last subject's last visit.

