11.4. Appendix 4: Premature Withdrawals & Handling of Missing Data

11.4.1. Premature Withdrawals

Element	Reporting Detail
General	
 Subject study completion (i.e. as specified in the protocol) was defined as subject who receives at least 25 days of study drug and completes the end of treatment biopsy and assessment. Withdrawn subjects may be replaced in the study. All available data from subjects who were withdrawn from the study will be listed and all available planned data will be included in summary tables and figures, unless otherwise specified.

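### The SAP drops out-of-window visits from every summary and analysis, safety included, although the protocol sets no window for Day 14 or Day 28

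*SAP*

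**What the plan says.** SAP 11.2.3 (Planned and Actual Time) takes visits that fall outside windows set by the protocol, which it equates with those logged as deviations, and rules that they "will be included in listings but omitted from figures, summaries and statistical analyses". The next block adds: "Unscheduled visits will not be included in summary tables". Unscheduled visits are kept out of figures too.

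The same section also undertakes to evaluate, where relevant, "The impact of any major deviation from the planned assessment times and/or scheduled visit days on the analyses and interpretation".

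The endpoints are tied to single days. The protocol's objectives table names the "composite clinical activity score at day 14 and day 28 in PV and existing lesions" and "Change from baseline in IFN mRNA signature in skin biopsies at day 28 in PV and existing CLE lesions". The Time and Events tables (Protocol 7.1, repeated in SAP Appendix 1) show Day 14 and Day 28 as bare days, and the SAP has no visit-window table.

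Protocol section 7 treats adherence to the Time and Events table as essential, while Protocol 5.4 tells sites to rebook a missed visit as soon as they can. SAP 4.1 leaves the tracking of deviations to a separate Protocol Deviation Management Plan. It also calls for a review, before database freeze, of deviations that could exclude data.

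**The concern.** The exclusion rule relies on a window that the protocol does not supply for the two visits that carry the efficacy and pharmacodynamic endpoints. Two analysts could apply it to the same data and arrive at different analysis sets, each claiming to follow the SAP. The deciding factor would be what was logged as a deviation. The trial is sponsor-unblinded, and Protocol 9.3.2 lets study team members take part in unblinded reviews, so the rule is better fixed in advance than left to the log.

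The second issue is scope. For a pharmacodynamic biopsy there is an argument for setting aside a sample taken at the wrong time. For safety there is not: a QTc or laboratory value recorded a few days early or late is still a safety observation, and a maximum or any-visit display should contain it. The rule makes no such distinction.

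The third is internal. The impact of timing deviations on an analysis can be assessed only if the data are in that analysis, or in a comparison version of it. The SAP plans no such version.

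**Working it through.** **The plan's own figure.** Protocol 9.2.1 has no power calculation. It gives a 95% interval for a safety event rate with 1 event in 15 under a flat Beta(1,1) prior. The equal-tailed limits of Beta(2,15) are 0.0155 and 0.302, which reproduces the stated 0.02 to 0.30. With no events in n subjects the upper limit is 1 − 0.025^(1/(n+1)). This gives 20.6% for n = 15 (stated 21%) and 24.7% for n = 12 (stated 25%). The protocol's own table therefore shows what it costs if a visit-based safety measure loses 3 of 15 subjects.

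**Step 1: where windows exist (Group B, Protocol 7.1.3).**

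| Item | Timing given | Tolerance |
|---|---|---|
| Lesion selection, pre-dose biopsies | Day -5 to -3 | range |
| Day 1 PK after dosing | 5 h ± 1 h | range |
| Day 14 (ECG, labs, vital signs, clinical score) | single day | none |
| Day 28 (biopsy, labs, vital signs, clinical score) | single day; biopsy 4 h after dose | none in days |
| Follow-up (ECG, labs) | Day 43 to 56 | range |

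**Step 2: the two readings for Day 14 and Day 28.** If no defined window means that nothing can fall outside one, the rule never acts there. If the bare day is itself the window, every visit on another day is removed. The text supports either. At follow-up there is no ambiguity: a visit after Day 56 that is logged as a deviation leaves the tables.

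**Step 3: what one off-day visit costs under the strict reading.**
- *Day 14 ECG.* Group B ECGs are scheduled at screening, Day 1 pre-dose, Day 14 and follow-up. Day 14 is the only one between first dose and follow-up. Losing it affects Tables 2.13 to 2.16, including the maximum QTc and maximum QTc change tables.
- *Vital signs.* After baseline they are scheduled only on Day 14 and Day 28, so one off-day visit removes half of a subject's post-baseline data from Tables 2.17 and 2.18.
- *Day 28 biopsy.* Both lesions are sampled at the same visit, so the active–placebo pair goes together. It leaves the IFN mRNA model (SAP 8.3.2) and the IHC and histology summaries (SAP 9.1.1).
- *RCLASI.* It is descriptive only (SAP 2.1 and 8.1.2), so the loss is from by-visit summaries.

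**Step 4: precision for paired endpoints.** The half-width of a paired 95% interval is t(0.975, n−1)/√n times the SD of the within-subject difference. Percentages use unrounded values.

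| Pairs | Half-width (SD units) | Against n = 15 |
|---|---|---|
| 15 | 2.145/3.873 = 0.554 | – |
| 14 | 2.160/3.742 = 0.577 | +4.3% |
| 12 | 2.201/3.464 = 0.635 | +14.7% |
| 10 | 2.262/3.162 = 0.715 | +29.2% |

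For the mRNA mixed model these factors are an approximation.

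**Step 5: how likely any loss is.** The documents give no off-day rate. Assuming independent visits with rate p, the chance of losing at least one of 15 is 1 − (1 − p)^15. For p = 5%, 10%, 20% and 30% this is 54%, 79%, 96% and 99.5%. The expected losses, 15p, are 0.75, 1.5, 3.0 and 4.5 pairs.

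**The case against.** The best defence is that the rule is harmless as written. It acts only on visits outside a defined window that are also recorded as deviations, and without a Day 14 or Day 28 window it has nothing to act on. Windows may also sit in the study reference manual or the deviation plan, neither of which is available here. Cream is applied daily by the investigator or a designee (Protocol 6.5), so frequent off-day visits look unlikely. This stands in part: the strict reading is one of two, and no rate can be claimed. But the SAP points to windows in the protocol, and Protocol 5.4 foresees rebooked visits. The defence also does not reach the follow-up visit, where a window exists, or the absence of a safety exception.

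Four stronger readings are tempting, and the documents do not support them.

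- *That the completion rule implies a visit tolerance.* Protocol 5.5 defines a completer as one who "receives at least 25 days of study drug and completes the end of treatment biopsy and assessment". Twenty-five days counts drug exposure. The synopsis and Protocol 4.1 tie the completer's biopsy to Day 28. A subject who misses three doses but attends on Day 28 loses nothing.
- *That the rule contradicts SAP 11.4.1*, where "all available planned data will be included in summary tables and figures". That bullet concerns withdrawn subjects and gives way to rules stated elsewhere, such as this one.
- *That the data disappear.* They stay in the listings.
- *That an adverse event could go unseen.* The adverse event tables do not depend on visits, abnormal values of potential clinical importance are listed (Listings 23 to 33), and the Safety Review Team sees safety data in-stream. What can happen is narrower: an abnormal value can be absent from a summary table.

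**Conclusion.** The point holds, as a cheap improvement. The exclusion rule is undefined for Day 14 and Day 28, covers the primary safety summaries without exception, and sits beside a promise to assess timing deviations that the exclusion makes hard to keep.

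The clearest consequence is for the QTc tables, where one off-day Day 14 visit can remove a subject's only scheduled ECG between first dose and follow-up. For the Day 28 pharmacodynamic comparison, losing 1, 3 or 5 of 15 pairs would widen a paired interval by about 4%, 15% or 29%. Those losses are assumed. They also take the planned Group B size of about 15; with fewer subjects each lost pair costs more (10 to 8 pairs: 0.836/0.715, about 17% wider). There is no precision target to miss, so this is lost information and avoidable ambiguity and does not invalidate the analysis.

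**What to change.** Amend SAP 11.2.3 as follows.

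1. **Safety.** Include all post-baseline values in the safety summaries whatever their timing, in particular the maximum QTc tables and the any-visit-post-baseline rows described in SAP 11.3.1. Extend this to assessments recorded as unscheduled.
2. **RCLASI, IFN mRNA, IHC and histology.** Either analyse an off-day assessment under its nominal visit, or state Day 14 and Day 28 analysis windows before the randomisation codes are released for analysis and before any treatment-labelled summary is reviewed. Show the actual day. A stated window has the advantage for biopsies that it sets a latest day, since the planned sample is 4 hours after a dose.
3. **Sensitivity.** Repeat the Day 28 mRNA analysis and the main summaries with on-time visits only. This also delivers the promised assessment of timing deviations.
4. **Population.** Do not restrict these analyses to completers. That would discard on-time Day 14 or Day 28 values from subjects with fewer than 25 days of drug, which the SAP now includes through the Safety population.

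The cost is SAP wording, a column for actual day and one extra run of the affected outputs. The downside is slightly more spread in actual assessment day, which the on-time-only analysis makes visible.
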